2. To compare the findings with a previously completed study using a population of adults with typical (i.e., normal) reading abilities (Cummene et al., in press).
3. To better understand how the speech production system contributes to reading performance. The information will help refine the currently accepted speech and reading neural models.

Study Design | Trial Design

Participant | Subject Criteria

Inclusion criteria. Thirty adults (i.e., ≥ 18 years of age) of either sex or identified gender with diagnosed or self-reported dyslexia will be recruited to participate in a within subjects repeated measures design. Thirty participants (18+) without dyslexia will also be recruited as a control

group. All participants will need to be proficient in English as the assessment materials are only available in English.

Reading disorders are rarely formally diagnosed because of many factors including but not limited to: timing in educational system for assessments, comorbidities with higher priority disorders (i.e., apraxia of speech, ADHD, etc.) and cost. Self-reported reading challenges are more accurate at identifying potential participants. Self-reported reading disorders will be confirmed/verified prior to enrollment via standardized reading measures.

Exclusion criteria. Participants must have no personal or family history of adverse reactions to anesthetics to complete all the conditions. Participant who cannot consume sugary products will be excluded. Additional exclusion criteria include: severe kidney disease; severe liver disease; treatment with class I antiarrhythmic drugs (such as mexiletine) or class III antiarrhythmic drugs (such as amiodarone); lack of integrity of oral mucosa; allergy to non-medicinal ingredients and preservatives (and related compounds) of Lidocaine Viscous, such as methylparaben, propylparaben, paraaminobenzoic acid, saccharin, artificial colours and flavour; concomitant use of another anaesthetic containing lidocaine or another amide; participant being pregnant or suspecting that she might be pregnant; negative pregnancy test is required for women of childbearing potential.

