3. Any participant reporting a personal or family history of adverse reactions to anesthetics will not be enrolled. If a participant reports any concerns or adverse reactions during the collection session, collection will immediately stop, and their participation discontinued.
4. If the participant is enrolled, they will be assigned a randomly generated identification number. All of their files and documents will be labelled with this number.
5. Each participant will also be randomly assigned to one of six possible task orders. Neither participants nor experimenters will be blinded to these conditions. This is documented in a hard-copy log.
6. Participants will be fit with an fNIRS cap to measure brain signals.
7. Then complete three computer generated tasks under four conditions (a, b and c will be randomized):
 - a. No sensory perturbation
 - b. Lollipop
 - c. Bite bar
 - d. Lidocaine – this condition will always be completed last.

8. The comparators to the lidocaine are no sensory perturbation, a candy lollipop and candy bite bar. All candy is obtained from the grocery store and are individually packaged. The lidocaine will be dispensed by a pharmacist and administered by the research team.
9. For the three computer generated tasks (randomly administered), accuracy and response time will be measured by the computer:
 - a. Task 1 (orthographic lexical decision): involves deciding whether a series of letters formulates a word or a nonword. Individuals will press the 'g' key if it is a word and the 'h' key if it is a nonword. Stimuli are single, monosyllabic, 4-7 letter length, words and nonwords.
 - b. Task 2 (phonological lexical decision): involves deciding whether a series of letters sounds out a word or a nonword. Individuals will press the 'g' key if it is a word and the 'h' key if it is a nonword. Stimuli are single, monosyllabic, 4-7 letter length, words and nonwords.
 - c. Task 3 (picture categorization): requires participants to make a judgement about whether a visually presented object is an animal or not. They will press 'g' if the object is an animal, and 'h' if it is not an animal.
10. Complete a short questionnaire rating and describing the numbness caused by the lidocaine (less than 5 minutes to complete).

Treatment

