The lidocaine condition will always be lastly completed so its effects will not interfere with the other conditions. Each participant will be asked to complete a questionnaire after collection to localize and rank their numbness on a provided schematic. And adverse events reported by the participant will be recorded on this document and reported immediately to the qualified investigator. After the collection session is over, the participant will be instructed to report to their nearest emergency room if they experience any reactions or adverse effects. Topical anesthetics in the mouth may impair swallowing. The numbness may also increase the risk of unintentional biting (e.g., cheek). The qualified investigator, an otolaryngology head and neck surgeon, will follow-up with the subject as she deems appropriate. All serious unexpected adverse drug reactions (SUSARs) will be reported to Health Canada as mandated per C.05.014 (1) of the FDR.

Budget Considerations

Participants will be offered a small honorarium (\$20.00) for taking part in the study.

Experiment Location

6-104, Clinical Sciences Building, University of Alberta.

Statistical Analysis

Given the between groups nature of the sensorimotor perturbation (i.e., lidocaine vs. no lidocaine groups), we will first run a $2 \times 2 \times 4 \times 2$ ANOVA with group (lidocaine vs. no lidocaine), task (spell vs. sound), word type (exception words, regular words, pseudohomophones, nonwords), and time (pre-lidocaine vs. post-lidocaine), as the factors of interest. If the 4-way interaction is significant, a series of mixed ANOVAs will be run to test the effect of sensorimotor perturbation for each of the reading tasks. The independent variables will be time (pre-perturbation vs. post-perturbation), word type (exception, regular, pseudohomophone, nonword) and group. An ANOVA was also be run to test the effect of the sensorimotor perturbation for the control picture categorization task, with the independent variables including time (pre-perturbation vs. post-perturbation) and group. The dependent variable will include response time and accuracy. Bonferroni corrected t -tests were used to explore significant effects of the lidocaine on task performance. No interim analyses are planned. The data will be analyzed when thirty subjects have participated.

Data | Documents

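### The per-task reading ANOVAs are run only if the 4-way interaction is significant, and a perturbation effect that is equal across word types contributes nothing to that interaction

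*Combined protocol and SAP*

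**What the plan says.** The Statistical Analysis section first fits a 2 x 2 x 4 x 2 ANOVA with group, task (spell, sound), word type (four levels) and time (pre, post). The next step is conditional: "If the 4-way interaction is significant, a series of mixed ANOVAs will be run to test the effect of sensorimotor perturbation", separately for each reading task, with time, word type and group as factors. The section does not say what happens if the 4-way term is not significant.

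The picture task has its own analysis with no such condition: "An ANOVA was also be run to test the effect of the sensorimotor perturbation for the control picture categorization task". Bonferroni-corrected "tests were used to explore significant effects of the lidocaine on task performance", but the effects that trigger them are not named. Response time and accuracy are both dependent variables. No alpha is given.

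Three other places bear on the point. Objective 1 asks for the effects of lollipop, bite bar and lidocaine on reading speed and accuracy in adults with dyslexia. The primary endpoint (Methodology) is reading response time and accuracy for each word type, with and without perturbation. The background describes the team's earlier lidocaine result by task: faster responses in the phonological task and no facilitation in the orthographic task. It does not say whether that result varied by word type.

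**The concern.** A 4-way interaction is a narrow question: does the group difference in pre-to-post change differ between the two tasks by an amount that itself depends on word type? Objective 1 asks something simpler, namely whether perturbation changes reading performance. Making the per-task reading tests depend on the narrow question means that a real, even large, effect can leave them unrun, while the control task is always tested. An effect confined to one task and similar across its word types is one such case. It fits the task-level description of the earlier result, although the documents neither establish nor exclude it.

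**Working it through.** **No plan figure to reproduce.** The documents give no alpha, effect size, SD, correlation or power. Everything numerical below is assumed, apart from the factor structure and the counts of 30.

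**Step 1: what the 4-way term measures.** For task t and word type w, let e(t,w) be the group difference in post-minus-pre change. Let d(w) = e(sound,w) - e(spell,w). The 4-way term is the set of deviations d(w) - mean(d).

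- Effect of -40 ms on all four word types in the sound task only: d = (-40, -40, -40, -40), deviations (0, 0, 0, 0).
- Effect of (-60, -60, -20, -20) ms in both tasks: d = (0, 0, 0, 0), deviations (0, 0, 0, 0).
- Effect of (-60, -60, -20, -20) ms in the sound task only: mean d = -40, deviations (-20, -20, +20, +20), sum of squares 1,600.

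In the first two cases the term is exactly zero, and effect size plays no part.

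**Step 2: how often the condition is met when the term is zero.** The F test has 3 and 3(2n-2) df with n per group. Assumptions: alpha 0.05, SD of change 80 ms per word type within a task, word-type correlation 0, 0.5 or 0.7, between-task correlation 0, 0.5 or 0.8, n = 15 or 30, and 20,000 simulated trials per cell. With an equal effect of 40 or 160 ms in one task, the condition was met in 4.7-5.3% of trials. A separate simulation with word-type variation identical in both tasks gave 4.7% (n = 15) and 4.9% (n = 30). With unequal word-type variances and no sphericity correction the rate was about 7%. These rates are per outcome. With two outcomes, the chance that at least one condition is met is 1 - 0.95² = 0.0975 if they are independent, and at most 0.10.

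**Step 3: illustration of the consequence (40 ms in one task, equal over word types, n = 30).** The SD of the word-type average is 80 x sqrt((1 + 3r)/4) = 40.0, 63.2, 70.4 ms at r = 0, 0.5, 0.7. The noncentrality is 40/(SD x sqrt(2/30)) = 3.87, 2.45, 2.20 on 58 df.

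| | r = 0 | r = 0.5 | r = 0.7 |
|---|---|---|---|
| Per-task test at 0.05, no condition | 97% | 67% | 58% |
| Condition met and per-task test significant at 0.05 | 4.8-5.1% | 3.2-3.5% | 2.7-3.1% |
| Per-task test at 0.0125, no condition | 90% | 45% | 36% |

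**Step 4: the case that favours the condition.** Take (-60, -60, -20, -20) ms in one task, n = 30. The noncentrality is (30/2) x 1,600 / [80² x 2(1-b)(1-r)], with b the between-task correlation. At b = r = 0 this is 24,000/12,800 = 1.875, giving 18%. At b = r = 0.5 it is 24,000/3,200 = 7.5, giving 61%. At b = 0.8 and r = 0.7 it is 24,000/768 = 31.25, giving over 99%. So the condition is met between 18% and more than 99% of the time. The mean effect is still 40 ms, so unconditional power at 0.0125 remains 90/45/36%. The conditional procedure, testing at 0.05, gives 17/22/30%, 32/42/50% and 70/64/58% at b = 0, 0.5 and 0.8 (r = 0, 0.5, 0.7 in each set). It is higher in 3 of the 9 cells, though the two procedures use different alpha levels.

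**Limit of steps 2 to 4.** They use two groups, lidocaine and no lidocaine, because that is the model written in the analysis section: "Given the between groups nature of the sensorimotor perturbation (i.e., lidocaine vs. no lidocaine groups"). The design says otherwise. Participants "will be recruited to participate in a within subjects repeated measures design", everyone completes the tasks under all four conditions (Methodology), and each participant receives lidocaine (Treatment). The algebra of step 1 does not depend on what group means. If it means dyslexia versus control, an effect equal in the two groups cancels as well. The power figures do depend on it and are illustrative only.

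**The case against.** **The effect is tested anyway.** The omnibus ANOVA contains group x time and group x task x time, and the Bonferroni t-tests are not restricted to the 4-way term, so they could be read as following up any significant lidocaine effect. This stands in part. A reader might infer that an effect equal across word types could not be detected, or that any follow-up of lower-order terms would have to be invented after seeing the data. The documents support neither inference. What remains is that the triggering terms are not named and that lower-order terms do not open the per-task ANOVAs.

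**Word type belongs to the question.** The primary endpoint is by word type, so an interaction with word type is relevant. This is true, but the endpoint asks for performance on each word type with and without perturbation. It does not ask only whether the word-type pattern of change differs between tasks.

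**The condition can do well.** Step 4 shows this, and a general loss of power cannot be claimed.

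**The group factor is the larger defect.** The paragraph must be rewritten for that reason in any case. This is fair, and it limits the power figures, but correcting the factor while keeping the condition would leave the problem in place.

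**Conclusion.** The point holds as a defect in a stated decision rule. The only written route to the per-task reading ANOVAs is a term that is zero whenever the perturbation effect is equal across word types, or varies by word type identically in both tasks. In those cases the route opens at about the nominal level per outcome: about 5% at an assumed alpha of 0.05 under sphericity, and about 7% in the unequal-variance example. The result of step 1 is certain. How often such effects occur cannot be judged from the documents, and the contrast of 97/67/58% with about 3-5% rests on assumed effects, SDs and correlations and on a two-group comparison that the design does not provide. The rule should be corrected before analysis. It does not by itself make the trial's question unanswerable.

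**What to change.** Delete the 4-way condition. For each reading task and each outcome, run the per-task ANOVA whatever the 4-way result. Keep word type and its interaction with the perturbation in the model, and report estimates by word type to match the primary endpoint.

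In the same paragraph:

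- State alpha, and apply a sphericity correction to the word-type terms.
- Pre-specify one perturbation test per task and outcome, with Holm or Bonferroni over 2 tasks x 2 outcomes = 4 tests (0.05/4 = 0.0125). If the three perturbations are tested separately the family is 12 (0.05/12 = 0.0042).
- Name the terms that trigger the t-tests.
- Define the perturbation factor to agree with the within-subject design.
- Report the lidocaine contrast as confounded with order (practice, fatigue), because "The lidocaine condition will always be lastly completed so its effects will not interfere with the other conditions". Removing the condition does not remove this confounding.

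Removing the condition is a change of wording. Redefining the perturbation factor is more work, but is needed regardless. The price is multiplicity: in the step 3 illustration, power falls from 97/67/58% at 0.05 to 90/45/36% at 0.0125 and 81/31/23% at 0.0042. The plan also says "The data will be analyzed when thirty subjects have participated". If that means 15 per group in the written model, power at 0.0125 is 0.535, 0.195 and 0.152. The number at analysis should be clarified alongside the 30 plus 30 in the inclusion criteria.

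### No planned test compares the reading tasks with the control picture task, so the listed analyses cannot support a reading-specific conclusion, although the data could

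*Combined protocol and SAP*

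**What the plan says.** Methodology has each participant "Then complete three computer generated tasks under four conditions". Two of the tasks are lexical decisions (orthographic and phonological). The third "requires participants to make a judgement about whether a visually presented object is an animal or not", using the same two response keys.

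Statistical Analysis then treats the tasks in two separate streams:

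- **Reading.** The main ANOVA is specified "with group (lidocaine vs. no lidocaine), task (spell vs. sound), word type" and time. Its task factor covers the two lexical decisions only. Separate mixed ANOVAs, one per lexical decision, follow only when the 4-way interaction reaches significance.
- **Pictures.** A further ANOVA is meant to "test the effect of the sensorimotor perturbation for the control picture categorization task". Its factors are time and group, and it has no task factor.

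The remaining follow-up is Bonferroni-corrected t-tests exploring lidocaine effects. No contrast between tasks is named. The document gives no significance level, effect size, standard deviation or power.

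**The concern.** Objective 3 asks how the speech production system contributes to reading. To attribute a change in response time or accuracy to reading, one has to separate it from a general change in speed, alertness or distraction caused by having something in, or done to, the mouth. The picture task is the only non-reading task and the plan itself labels it the control. It can serve that purpose only if its effect is compared with the effect in reading.

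Two features of the document raise the stakes. The background section reports the earlier results task by task, as facilitation in one task and none in the others, and Objective 2 is to compare the new findings with a previous study in typical readers. Also, lidocaine always comes last, so any comparison of lidocaine with an earlier condition includes practice and fatigue. A direct comparison with pictures would remove the part of these that all tasks share; two separate ANOVAs do not.

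**Working it through.** **Structure.** The main ANOVA is 2 × 2 × 4 × 2 = 32 cells, and its task factor covers 2 of the 3 tasks. Word type does not exist for pictures, so pictures could not enter that ANOVA as written. Going through every listed analysis (main ANOVA, per-task follow-ups, picture ANOVA, t-tests), none contains a reading-versus-picture term. This part needs no numbers.

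**Size, as an illustration.** There is no figure in the plan to reproduce. Assumptions that are not in the document: two-sided 5% level; paired t-tests on each person's perturbed-minus-unperturbed change; the same true standardized change (dz) in all three tasks; equal correlation r between the changes in any two tasks; each test run unconditionally; 40,000 simulated studies per setting. N = 30 is the size of one reader group and the number at which the plan says data will be analysed.

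Percentage of studies with at least one reading task significant and pictures not significant, N = 30:

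| dz | power per task | r = 0.3 | r = 0.5 | r = 0.7 |
|---|---|---|---|---|
| 0.2 | 18.5 | 22.0 | 18.3 | 13.9 |
| 0.3 | 35.5 | 29.8 | 24.9 | 18.9 |
| 0.4 | 56.3 | 29.5 | 24.8 | 18.9 |
| 0.5 | 75.4 | 20.4 | 17.5 | 14.0 |
| 0.6 | 88.8 | 10.1 | 9.5 | 7.9 |

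The range is about 8% to 30%. With N = 60 and dz = 0.6 (power 99.5% per task) it is 0.4% to 0.5%.

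**Direct contrast, same data.** Take each person's change in one reading task minus the change in pictures. It rejects in about 5% of studies in every setting. That is the rate for one contrast. Two unadjusted contrasts, one per reading task, reject at least once in about 9%; testing each at 0.05/2 = 0.025 brings this to just under 5%.

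**Pooled or per task.** Suppose dz = 0.5 in one reading task and zero in the other two tasks, with r = 0.5 and N = 30.

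- Task-specific contrast: 0.5 / √(2(1 − 0.5)) = 0.5, power 75%.
- Average of both reading tasks minus pictures: mean 0.5/2 = 0.25; variance (1 + 0.5)/2 + 1 − 2(0.5) = 0.75; 0.25/√0.75 = 0.289, power 33%.

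The background section reports one-task effects (lidocaine in the phonological task, lollipop in the orthographic task), so a pooled contrast would dilute the kind of effect the earlier study found.

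**Multiplicity.** Two reading tasks × three perturbations × two outcomes = 12 contrasts. Unadjusted and independent, 1 − 0.95^12 = 46%. Bonferroni gives 0.05/12 = 0.0042 per contrast, at which the 75% above falls to 37%.

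**The case against.** **The plan's own condition limits the error.** The per-task reading ANOVAs run only after a significant 4-way interaction. An effect that is additive and equal across tasks creates no such interaction, so they would run in about 5% of studies and the misleading pattern reached by that route is capped near 5%. This stands, and it is why the 8% to 30% is labelled as unconditional. It is not full protection. Lower-order terms of the main ANOVA can still be read beside the picture ANOVA, and the interaction includes a lidocaine/no-lidocaine group although every participant receives lidocaine. The condition also does not supply the missing comparison.

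**No inference rule is stated.** The plan does not say that specificity will be read from one significant and one non-significant result. Objectives 1 and 2 do not need a picture contrast, and the primary endpoint is defined by word type. This also stands: the plan lacks a test, but it does not declare a wrong one. The concern is confined to any claim of reading specificity under Objective 3.

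**Stronger readings that the document does not support.** A reader might infer that a reading-specific effect cannot be shown at all. That is true of the listed tests only: the same people do all three tasks, so the data allow the comparison. A reader might call pictures the study's only control. They are the only non-reading task, but there is also a no-perturbation condition, random order of the first three conditions, a group without dyslexia, and 12 two-session participants for order and fatigue. None of these separates a reading effect from a general one. Finally, treating the three tests as independent gives (1 − (1 − p)²)(1 − p) = 19.2% at power p = 0.8 and 37.5% at p = 0.5. Independence does not fit a design in which the same people do every task.

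**Conclusion.** The concern holds in this limited form: the Statistical Analysis section contains no comparison of reading with the control picture task, so its tests cannot support a conclusion that an effect is specific to reading. That follows from the factor lists and rests on no assumed number. The size of the risk does rest on assumptions: about 8% to 30% at N = 30 if separate results are compared informally, less if the 4-way condition is followed, and under 1% at very high power. The change should be made before analysis. The lidocaine/no-lidocaine and pre/post factors, which do not match the design, are a wider problem; the new contrast has to be written for the actual design.

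**What to change.** Add to Statistical Analysis, for each reading task separately, the within-person contrast: (perturbation minus no perturbation in that reading task, averaged over word type) minus (perturbation minus no perturbation in pictures).

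- Use the four actual conditions in place of pre/post, and reader group (dyslexia or control) in place of lidocaine/no lidocaine. State whether each contrast is estimated within the dyslexia group, across both groups, or as a difference between groups.
- Do this for response time and for accuracy. Fix the response-time scale in advance (for example log), because baseline speed may differ between tasks and equal effects on one scale are not equal on another.
- Control multiplicity across the contrasts, for example by Holm or Bonferroni. Naming a small confirmatory set and calling the rest exploratory would limit the loss of power.
- Claim a reading-specific effect only where the relevant contrast is significant, and report its estimate and confidence interval.
- Keep the separate picture ANOVA as description if wanted.

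Cost: a rewrite of this part of the analysis section and a few extra contrasts on data already being collected, with no new participants or tasks. The downside is a stricter standard: some true one-task effects will be reported without a specificity claim, particularly if all 12 contrasts share one adjustment.

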
(2014) reported that sensory cueing approaches (which place emphasis on the relation between movements and auditory and somatosensory information via auditory, and touch, pressure, kinesthetic and proprioceptive cues) are the most effective for treatment of CAS. Such results suggest that sensory cueing approaches either target the underlying impairment directly (i.e. restorative) or compensate for deficits (i.e. compensatory). The identification of sensory difficulties in children with CAS is important to understand speech characteristics and treatment efficacy in this population. These findings warrant additional investigations to understand if and to what extent somatosensory processing contributes to speech production and reading deficiencies in healthy and impaired adult and pediatric populations.

We have also previously attempted to determine the influence of speech production feedback on reading performance by measuring reading performance in adults while adding an additional motor component (i.e., lollipop, bite bar, lidocaine). These somatosensory perturbations have the potential to alter and/or decrease the sensory feedback from the articulators in the mouth.

We found that the lollipop had a facilitatory effect (i.e., faster response times) in the orthographic lexical decision tasks but no effect on the phonological lexical decision tasks or picture categorization tasks. In contrast, the lidocaine had a facilitatory effect (i.e., faster response times) in the phonological lexical decision tasks, but no facilitatory effects on the orthographic lexical decision tasks or picture categorization. Finally, the bite bar did not impact performance in any of the three tasks. However, we do not know if these effects (i.e., lollipop, bite bar, lidocaine) hold for an adult population with reading disorders.

The investigational product we are requesting approval to use is Lidocaine Hydrochloride Oral Topical Solution 2% USP. This oral topical anesthetic will temporarily numb the participant's articulators. This clinical trial will be conducted in compliance with this described protocol, GCP and the applicable regulatory requirement(s).

Purpose | Objectives

1. To determine the effects of three different somatosensory perturbations (i.e., lollipop, bite bar, lidocaine) on reading performance (i.e., speed, accuracy) in adults with dyslexia.

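### The trial asks whether a pattern made up mostly of absent effects holds in dyslexia, but the plan has only lidocaine-centred significance tests and estimates neither the nine contrasts nor the reader-group difference.

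*Combined protocol and SAP*

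**What the plan says.** **Earlier results (background, before Purpose | Objectives).** Three perturbations were tried on three tasks in adults.

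- Lollipop: responses were quicker on the orthographic task. For the other two tasks the text reads "no effect on the phonological lexical decision tasks or picture categorization tasks".
- Lidocaine: responses were quicker on the phonological task. For the other two tasks the text reads "but no facilitatory effects on the orthographic lexical decision tasks or picture categorization".
- Bite bar: "the bite bar did not impact performance in any of the three tasks".

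The background then states the open question: "we do not know if these effects (i.e., lollipop, bite bar, lidocaine) hold for an adult population with reading disorders".

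**Objectives.** Objective 1 is to determine the effects of all three perturbations on reading speed and accuracy in adults with dyslexia. Objective 2 is to compare the findings with the completed study in typical readers.

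**Sample (Participant | Subject Criteria).** "Thirty adults (i.e., ≥ 18 years of age) of either sex or identified gender with diagnosed or self-reported dyslexia", plus thirty controls without dyslexia.

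**Statistical Analysis.** The first step is a four-way ANOVA on group (lidocaine or none), task (the two reading tasks), word type and time (before or after lidocaine). Mixed ANOVAs for the reading tasks follow only if the four-way interaction is significant. The picture task has its own ANOVA, which is not conditional. Bonferroni-corrected t-tests "were used to explore significant effects of the lidocaine on task performance". The documents give no interval estimate, no rule for a non-significant result, and no alpha, target effect size or sample-size justification.

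**The concern.** Most of the earlier pattern consists of cells where nothing, or no facilitation, was found. The bite bar is named in the question although all three of its results were null, so the null cells are part of what is to be checked. A test against zero can reject a null but cannot support one, and a small or noisy sample fails to reject easily.

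The error can run in two directions. In a cell that was null before, a missed true effect would look like replication. In either of the two facilitated cells, a missed true effect would look like a difference between dyslexic and typical readers. The picture task adds weight because the plan calls it a control task: attributing a perturbation effect to reading depends partly on little happening there.

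The plan also stops short of the objectives. Its group factor is lidocaine versus none, not dyslexia versus control, and its time factor is built around lidocaine. Neither the lollipop and bite-bar contrasts nor the reader-group comparison is named.

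**Working it through.** **1. Count of cells, from the background.**

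| Perturbation | Orthographic | Phonological | Picture |
|---|---|---|---|
| Lollipop | faster | no effect | no effect |
| Lidocaine | no facilitation | faster | no facilitation |
| Bite bar | no effect | no effect | no effect |

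3 × 3 = 9 cells: 2 facilitated and 9 − 2 = 7 not. The two lidocaine cells are described only as lacking facilitation, which does not rule out slowing. That leaves 7 − 2 = 5 plain no-effect statements.

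**2. Objectives set against the analysis.**

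| Needed | Provided in Statistical Analysis |
|---|---|
| Lidocaine effect by task (3 cells) | ANOVA tests; reading-task follow-up only after a significant four-way interaction; t-tests of significant effects |
| Lollipop effect by task (3 cells) | No contrast named |
| Bite-bar effect by task (3 cells) | No contrast named |
| Dyslexia versus typical readers | No such factor named |
| Size and precision of any effect | No interval named |

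The follow-up ANOVAs do speak of time before and after perturbation. However, the section opens by defining the perturbation as lidocaine versus no lidocaine, so the natural reading is lidocaine again.

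**3. What non-significance could hide (illustration).** The plan gives no power figure to reproduce. Assumptions: a single paired comparison, two-sided α = 0.05, n = 30 in a reader group, and true effect d in units of the SD of the within-person difference. The values of d are chosen to show a range.

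Power = P(|T| > t₀.₉₇₅,₂₉), where T is noncentral t with 29 df and noncentrality d√30, and t₀.₉₇₅,₂₉ = 2.045.

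| d | d√30 | Power | Missed |
|---|---|---|---|
| 0.2 | 1.10 | 0.185 | 81% |
| 0.3 | 1.64 | 0.355 | 64% |
| 0.4 | 2.19 | 0.563 | 44% |
| 0.5 | 2.74 | 0.754 | 25% |

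A Bonferroni correction raises the miss rate. The number of comparisons is not stated. With 3, 4 or 9, power at d = 0.4 falls to 0.378, 0.336 or 0.234.

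**4. Precision.** The 95% half-width for one cell is t₀.₉₇₅,₂₉/√30 = 2.045/5.477 = 0.37 SD. For the dyslexia-minus-control difference with 30 per group and equal SDs, it is t₀.₉₇₅,₅₈ × √(2/30) = 2.002 × 0.258 = 0.52 SD.

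**5. Comparing significance labels between groups.** Suppose both groups have the same true effect of 0.4 SD and are tested separately. The chance that one is significant and the other is not is 2 × 0.563 × 0.437 = 0.49. Differing labels are therefore weak evidence of a group difference.

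**6. What an equivalence claim would need.** Two one-sided 5% tests, true difference zero, n = 30:

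| Margin (SD) | 0.2 | 0.3 | 0.4 | 0.5 | 0.6 |
|---|---|---|---|---|---|
| Power | about 0% | 5% | 38% | 70% | 88% |

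80% power is reached at a margin of about 0.55 SD.

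**The case against.** **No objective is to prove absence of effect.** This is true of the wording, and the carry-over question stands in the background. But objective 2 compares findings with a study whose results were mostly null, and the question names the bite bar, which had nothing but nulls. Interpreting those cells cannot be avoided.

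**The documents do not say that non-significance will be reported as no effect.** This stands. A reader might infer that it would be, since the background describes its own earlier nulls that way. The plan contains no reporting rule either way, so the most that can be said is that such results could be read so. A reader might also infer that seven earlier results are firm nulls; two are worded only as no facilitation.

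**The power figures describe a simpler test than the planned one.** This stands too. The gate on the four-way interaction was not modelled, and every effect size and alpha is assumed. The figures show what 30 readers can resolve in one contrast; they are not the operating characteristics of the plan.

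**A mandatory equivalence margin could be unreachable.** This is correct. At 0.2 SD, for example, 30 readers have essentially no power, so almost every truly null cell would be inconclusive. Intervals alone expose the uncertainty, so a formal margin is a choice and not a requirement.

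**The deeper fault is the mismatch between the analysis and the four-condition within-subject design.** This is fair, and the two should be repaired together. Correcting the factors alone would still leave no estimates and no guidance on non-significant cells.

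**Conclusion.** The concern holds in limited form. The analysis plan does not estimate what objectives 1 and 2 ask for: as written, it names no lollipop or bite-bar contrast, no dyslexia-versus-control contrast and no interval. A non-significant cell is therefore left open to being read as no effect, or as a departure from typical readers.

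The stronger claim, that the trial will report non-significance as no effect, is not supported, because the documents are silent on reporting.

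The count of cells and the content of the analysis section come directly from the documents. The miss rates (81% to 25% over 0.2 to 0.5 SD) and half-widths rest on an assumed paired t-test with 30 readers per group analysed. The plan says analysis starts when thirty have participated, although thirty per group are to be recruited; fewer per group would make precision worse. This should be corrected before analysis, but it does not call for a larger sample.

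**What to change.** In Statistical Analysis, name the nine contrasts: each perturbation against no perturbation, on each task. For every one, significant or not, report the mean difference with a 95% interval in each reader group, and the dyslexia-minus-control difference with its interval. Do this for response time and for accuracy. The estimates should not depend on the four-way interaction.

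Base any statement that an effect holds, or differs from typical readers, on those intervals. Do not describe a non-significant result as no effect.

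A formal equivalence margin is optional. If one is used, fix it before analysis and state what 30 readers can support: about 0.55 SD of the within-person difference for 80% power when the true difference is zero.

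The cost is some wording and one more table, with no new participants or procedures. The real downside is that many cells may have to be reported as inconclusive.
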